## **6.5. Patient Disposition**

A description of participant disposition will be provided, including a summary of the number and percentage of participants entered into the study, enrolled in the study, and treated, as well as the number and percentage of participants completing the study (participants who receive at least

1 dose of study drug and have at least 1 postbaseline assessment), or discontinuing (overall and by reason for discontinuation). A summary of important protocol deviations will be provided.

[figure not shown]
## 6.6. Patient Characteristics

Demographic data are collected and reported to demonstrate that the study population represents the target patient population. A summary of baseline demographics and disease characteristics, historical diagnoses, pre-existing conditions, and prior therapies will be reported using descriptive statistics. Other participant baseline characteristics will be summarized by group as deemed appropriate.

## 6.7. Efficacy and Health Outcome Analyses

### 6.7.1. Primary Endpoint

The primary comparison of interest is the proportion of participants achieving HiSCR response at Week 16. The HiSCR (Kimball et al. 2014; Kimball et al. 2016b) is defined as at least a 50% reduction in the total abscess and inflammatory nodule count (sum of abscesses and inflammatory nodules [AN count]) with no increase in abscess count (A count) and no increase in draining fistulae count (DF count) relative to baseline.

The primary comparison to establish superiority of LY3041658 over placebo using a composite estimand where the intercurrent events of premature discontinuation and use of prohibited medication are part of the response definition. The composite endpoint will be analyzed using logistic regression on the mITT and PPS population with treatment group in the model. The treatment difference and 95% CIs will be reported.

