1.3. Schedule of Activities (SoA)

Table 1. Schedule of activities for the Screening Period and Treatment Period 1 of Study I7P-MC-DSAD

Visit 1 procedures may be conducted over more than 1 day as long as all activities are completed within the allowable visit tolerance.

For procedures at an early termination visit, see ETV in Table 2.

For procedures at an unscheduled visit, see V997 in Table 2. Unscheduled visits are for participants needing rescue therapy or incision and drainage.

For procedures at an unscheduled	visit, s	ee v 95	9 / IN I	abie 2.	Unsch	eduled	i visits	are 101	partic	ipants n	needing rescue therapy or incision and drainage.
Visit number	V1	V2	V3	V4	V5	V6	V7	V8	V9	V10	Comment
Weeks from randomization	-5	_	2	4	6	8	10	12	14	16	
Study day	—	1	15	29	43	57	71	85	99	113	
Visit interval tolerance (days)	≤35	_	±2	±2	±2	±2	±2	±2	±2	±2	
Fasting visit		X								X	
Informed consent	X										
Inclusion and exclusion criteria, review and confirm	X	X									
Demographics	X										
Preexisting conditions and medical history	X										
Prespecified medical history (indication and history of interest)	X										
Prior treatments for indication	X										Relevant surgical history
Concomitant medications	X	X	X	X	X	X	X	X	X	X	
Adverse events	X	X	X	X	X	X	X	X	X	X	For AESIs, additional data are collected (Section 8.3.6).
Substance use (alcohol, caffeine, tobacco)	X										
Surgical interventions related to HS		X	X	X	X	X	X	X	X	X	
Physical Evaluation											
Height	X										Without shoes.
Weight	X									X	
Vital signs	X	X	X	X	X	X	X	X	X	X	Blood pressure, body temperature, pulse rate. Vital signs should be measured after participant has been sitting for at least 5 minutes.

Table 1. Schedule of activities for the Screening Period and Treatment Period 1 of Study I7P-MC-DSAD

Visit 1 procedures may be conducted over more than 1 day as long as all activities are completed within the allowable visit tolerance.

For procedures at an early termination visit, see ETV in Table 2.

For procedures at an unscheduled visit, see V997 in Table 2. Unscheduled visits are for participants needing rescue therapy or incision and drainage.											
Visit number	V1	V2	V3	V4	V5	V6	V7	V8	V9	V10	Comment
Weeks from randomization	-5	_	2	4	6	8	10	12	14	16	
Study day	_	1	15	29	43	57	71	85	99	113	
Visit interval tolerance (days)	≤35	_	±2	±2	±2	±2	±2	±2	±2	±2	
Fasting visit		X								X	

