2.2. Background

Hidradenitis suppurativa (HS) or acne inversa is a chronic, recurrent, inflammatory, debilitating skin disease usually presenting after puberty with painful, deep, inflamed lesions in the apocrine gland-bearing areas of the body, commonly the inguinal axillaries, and anogenital regions (Zouboulis et al. 2015; Zouboulis 2006).

Even when HS lesions heal, permanent fibrosis, dermal contractures, and induration of the skin frequently occur. These tissue changes can be physically, psychologically, and cosmetically debilitating. As tissue damage accumulates over time, patients frequently develop low self-esteem and loneliness (Kouris et al. 2016) and become socially withdrawn, unable to maintain employment, and susceptible to poverty, depression, and suicidality (Vekic and Cains 2017).

There is currently no uniformly effective single therapy for HS. Numerous treatment modalities are employed, including antibiotics, retinoids, hormones, immunosuppressive and anti-inflammatory agents, neurotoxins, radiotherapy, and surgery. The tumor necrosis factor inhibitor adalimumab has been approved in the United States, Europe, and Australia for the treatment of moderate-to-severe HS (Zouboulis et al. 2015; Kimball et al. 2016a; Vekic and Cains 2017). Yet substantial unmet medical needs remain, since adalimumab fails either to treat many patients adequately or to maintain treatment effect over time (Kimball et al. 2016a). Patients with HS are appropriate for a novel investigational product (IP) with immunomodulating properties.

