5.2. Exclusion Criteria

Participants will be excluded from study enrollment if they meet any of the following criteria within the screening period, unless otherwise specified:

Skin diseases and conditions

- [9] Have more than 20 draining fistulae.
- [10] Have had surgical treatment for HS in the last 4 weeks prior to baseline (the randomization visit).
- [11] Have active skin disease or condition (for example, bacterial, fungal or viral infection) that could interfere with assessment of HS.

Prior or concomitant therapy

- [12] Are unwilling or unable to stop treatment with topical antibiotics for HS 14 days prior to baseline (the randomization visit) and for the duration of the study.
- [13] Have received any biologic agent for treatment of HS (for example, adalimumab) at any time.
- [14] Have received any biologic agent (such as monoclonal antibodies, whether investigational or marketed) for any indication other than HS within 3 months or 5 half-lives (whichever is longer) before baseline (the randomization visit).
 - Note: Participants may be considered for enrollment if they have stopped receiving a biologic agent for an indication other than HS at least 3 months or 5 half-lives (whichever is longer) before baseline (the randomization visit) and if all other eligibility criteria are met.
- [15] Have received any systemic nonbiologic immunosuppressive medication for any indication within 28 days before baseline (the randomization visit).

[16] Have received oral opioids for HS-related pain within 14 days before baseline (the randomization visit) or are anticipated to receive oral opioids for HS-related pain during the study.

- Note: Participants may be considered for enrollment if they have stopped receiving oral opioids for HS-related pain more than 14 days before the baseline visit and if all other eligibility criteria are met.
- [17] Have received any systemic (including oral) antibiotic or anti-infective treatment within 28 days prior to baseline (the randomization visit), unless as required for latent tuberculosis infection (LTBI) treatment (see criterion #25) or prescribed for HS (see criterion #8).
- [18] Have a history of chronic alcohol abuse, IV drug abuse, or other illicit drug abuse within 1 year prior to the screening visit.

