6.5.2. Permitted Concomitant Therapy

The following will be required as concomitant therapy during the study:

- one of the following over-the-counter topical antiseptics to be used on body areas affected with HS lesions:
 - o chlorhexidine gluconate
 - o triclosan
 - benzoyl peroxide, or
 - o dilute bleach in water.

Other medications are permitted during the study, including, but not limited to, these:

- wound care dressings: alginates, hydrocolloids, and hydrogels
- oral antibiotics: Participants on a stable dose of an oral antibiotic for HS before screening must remain on the same stable dose throughout the study, unless a change is required for the participant's safety. The permitted oral antibiotics will be recorded on the eCRF as concomitant medications.
- CBD products derived exclusively from hemp: Participants who use these products must be on a stable dose before the randomization visit and remain on the stable dose throughout the study.

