6.5.4. Prohibited Concomitant Therapy

The following will be prohibited as concomitant therapy during the study:

- topical antibiotics for HS
- any biologic agent, whether marketed or investigational
- any non-biologic systemic immunosuppressant
- oral opioids for HS-related pain, and
- cannabis (marijuana).

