9.1.1. Estimands

The study will compare LY3041658 with placebo in participants with HS.

The primary comparison of interest is the difference in proportion of participants who achieve HiSCR response at Week 16. The primary objective is to demonstrate superiority of LY3041658 versus placebo.

The primary comparison will be assessed using a composite estimand where the intercurrent events of premature discontinuation and use of prohibited medication are part of the response definition.

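### HS surgery before Week 16 is not covered by the composite estimand, so lesions removed by surgery can count towards HiSCR response

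*SAP*

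**What the plan says.** SAP 6.7.1 sets up the primary comparison as a composite in which "the intercurrent events of premature discontinuation and use of prohibited medication are part of the response definition". SAP 6.1.1 has the same rule, and Protocol 9.1.1 agrees: "premature discontinuation and use of prohibited medication are part of the response definition". No third event is named anywhere.

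Protocol 6.5.4 opens with "The following will be prohibited as concomitant therapy during the study" and has five entries: topical antibiotics for HS, biologics, "any non-biologic systemic immunosuppressant", oral opioids for HS pain, and cannabis. All are drugs or substances. Protocol 6.5.2 is open-ended on the permitted side: "Other medications are permitted during the study, including, but not limited to, these".

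The protocol nevertheless expects surgery. Its background section says "Numerous treatment modalities are employed, including antibiotics, retinoids, hormones, immunosuppressive and anti-inflammatory agents, neurotoxins, radiotherapy, and surgery". Exclusion criterion 10 bars people who had HS surgery in the 4 weeks before baseline. The Schedule of Activities has a row "Surgical interventions related to HS", marked at every visit from baseline (Visit 2) to Week 16 (Visit 10). No efficacy section of the SAP uses that record.

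HiSCR itself compares Week 16 lesion counts with baseline. AN must fall by half or more, and neither abscesses nor draining fistulae may increase. It sets no condition on how lesions went away.

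**The concern.** Excising a region lowers the abscess, nodule and fistula counts from which HiSCR is built. The exclusion before baseline suggests that recent surgery was thought to interfere with the assessment. The composite already treats use of prohibited therapy as failure. Surgery for uncontrolled disease is failure in the same sense, yet it can be scored as success.

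At stake is the primary contrast in a small trial, where a few reclassified participants move the estimate visibly. Change in AN count at Week 16, a secondary endpoint, is exposed in the same way because the counts after surgery are used as they stand.

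**Working it through.** **1. The plan's own figure.** Protocol 9.2 claims at least 80% power at two-sided 0.05 with about 63 randomized 2:1 (42 and 21) and about 45 completing 16 weeks. The assumed HiSCR rates are redacted, so this cannot be reproduced. That is not an error in the plan.

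**2. Following one participant through the rules.** Take someone who has an excision in Treatment Period 1, stays on study drug and attends Week 16.

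| Rule | Effect |
|---|---|
| Composite (Protocol 9.1.1; SAP 6.1.1, 6.7.1) | No discontinuation and no prohibited medication, so not nonresponse |
| Reasons to stop study drug (Protocol 7.1.1) | Surgery is not named, though the list is not exhaustive |
| Withdrawal for another effective agent (Protocol 7.2) | Concerns a therapeutic agent; does not clearly reach surgery |
| Missing data (SAP 6.4) | Not triggered; the counts are observed |
| Background therapy (SAP 6.1) | Changes are disregarded, which points to using observed counts |
| Per Protocol Set (SAP 6.3.1) | Defined by missed doses only; surgery does not remove anyone |

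By default, Week 16 HiSCR is computed from the counts left after surgery.

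**3. Lesions needed.** The AN part of HiSCR needs a fall of at least AN/2. Inclusion criterion 6 sets the minimum AN at 4. At AN 4, removing 2 lesions gives 2/4 = 50%. At AN 6 it takes 3, and at AN 10 it takes 5.

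**4. Weight of one reclassified participant.**
- Protocol sizes: placebo 1/21 = 4.8 points; active 1/42 = 2.4 points.
- SAP sizes (17 and 34): placebo 1/17 = 5.9 points; active 1/34 = 2.9 points.

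**5. Direction.** With *a* active and *b* placebo participants reclassified, the observed difference (active minus placebo) shifts by *a*/42 − *b*/21.
- One in each arm: 2.4 − 4.8 = −2.4 points.
- One on placebo only: −4.8 points.
- Two on active only: 2/42 = +4.8 points.
- The same share of each whole arm (2 of 42 and 1 of 21): no shift.
- The same share *s* of nonresponders in each arm: the difference is multiplied by (1 − *s*).

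**6. Illustration under assumed rates.** No surgery frequency is given, so everything here is assumption. Placebo rates of 20, 30 and 40% were taken. The active rates that give 80% power with 21 against 42 (pooled z test) are 55.8, 66.6 and 75.8%. If surgery turns a share *s* of nonresponders into responders, the observed rate is *p* + (1 − *p*)*s*. At placebo 30% and *s* = 5% in both arms: placebo 0.30 + 0.70 × 0.05 = 0.335; active 0.666 + 0.334 × 0.05 = 0.683; difference 0.348 instead of 0.366.

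| Share of nonresponders converted (placebo / active) | Observed difference, points (placebo 20 / 30 / 40%) | Power, % |
|---|---|---|
| 0 / 0 | 35.8 / 36.6 / 35.8 | 80 / 80 / 80 |
| 5% / 5% | 34.0 / 34.8 / 34.0 | 74 / 76 / 77 |
| 10% / 10% | 32.2 / 32.9 / 32.2 | 69 / 71 / 73 |
| 10% / 5% | 30.0 / 31.3 / 31.0 | 62 / 66 / 69 |

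**The case against.** Several points limit how far this goes.

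- **Drug treatments.** A reader might infer that every non-antibiotic HS treatment listed in Protocol 2.2 escapes the composite. That is wrong. Biologics and systemic immunosuppressants are prohibited and so already count as nonresponse. For another agent demonstrated effective in HS, Protocol 7.2 has discontinuation come before the new agent, and SAP 6.1 makes discontinuation nonresponse. That route is permissive and depends on what counts as demonstrated, but it exists. Intensifying an existing treatment is arguably covered by the rule that changes in background therapy are disregarded. Treating these drugs differently is a debatable estimand choice, so they belong in a sensitivity analysis.
- **Direction.** A reader might infer that surgery falls mainly on placebo and hides an effect. This is plausible if the drug works, but nothing in the documents shows it. Surgery on the active arm would inflate the difference.
- **Automatic response.** Removing lesions does not by itself make a responder. The full HiSCR definition must be met and the participant must not have discontinued.
- **Frequency.** The documents give none. Excisional surgery within 16 weeks may be uncommon.
- **The surgical record.** The row is also marked at the unscheduled visit, which exists for rescue therapy or incision and drainage. It may therefore include permitted incision and drainage, and the documents do not show that the field separates the two.
- **Lesion procedures.** Protocol 6.5.3 allows incision and drainage or intralesional steroid on up to 2 lesions at a visit, which is the number needed at AN 4. A rule confined to surgery leaves this route open in the primary analysis.
- **Unseen documents.** SAP 6.11 refers to a separate list of important deviations. It might mention surgery, but it would not define the estimand.

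All of these stand as limits. None supplies a rule for scoring Week 16 HiSCR after HS surgery.

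**Conclusion.** The gap is real and specific. HS surgery between first dose and Week 16 is anticipated and recorded, but it is neither prohibited nor an intercurrent event, and the counts it leaves behind are scored as observed. Each participant reclassified in this way moves the arm rate by 4.8 points (placebo) or 2.4 points (active) at the protocol's sample size, and by 5.9 or 2.9 points at the SAP's. These figures take the planned arm sizes as denominators. The total effect and its sign depend on how many cases occur and in which arm, which the documents do not give; the power figures above are assumption ranges only. Neither a claim about all unlisted drug treatments nor a claim that the bias must run against the study drug is supported. The change should be made because it is cheap and follows the logic of the existing composite, with moderate confidence that it will matter in practice.

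**What to change.** 1. In Protocol 9.1.1 and SAP 6.1.1 and 6.7.1, add HS surgery between first dose and Week 16, other than the incision and drainage named in Protocol 6.5.3, to the composite as HiSCR nonresponse.
2. For change in AN count, set counts after surgery to missing and handle them under SAP 6.4. Name the method, for example the last observation before surgery, since 6.4 leaves the choice open.
3. Flag cases from the surgical-intervention record. Confirm that incision and drainage can be told apart from other surgery; if the field does not show this, settle it by blinded review of the entries.
4. Add a sensitivity analysis that also scores as nonresponse any participant with a lesion procedure under Protocol 6.5.3, or with a newly started HS-directed treatment that is neither prohibited in 6.5.4 nor covered by the discontinuation route in 7.2. Concomitant medications are already collected with reason and dates.

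The cost is estimand wording, one derived flag with a check of the surgical entries, and one extra analysis. It should be fixed before unblinding. Response rates in both arms may be slightly lower. The change concerns outcome scoring only and takes no position on which treatments participants may receive.

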9.2. Sample Size Determination

Approximately 100 patients will be screened to achieve approximately 63 participants randomized in a 2:1 ratio to one of two treatment groups:

approximately 42 participants randomized to LY3041658, and

approximately 21 participants randomized to placebo.

For all randomized patients, approximately 45 patients are expected to complete the 16 weeks' treatment period. This sample size provides at least 80% power to the primary endpoint of HiSCR response. This calculation is a 2-sided test for superiority of LY3041658 compared to placebo on HiSCR response rate with significance level of 0.05 CCl

CCI

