**5.2. Method of Assignment to Treatment**

Subjects who meet all criteria for enrollment will be randomized in a 2:1 ratio to double-blind treatment at Visit 2. Assignment to treatment groups will be determined by a computer-generated random sequence using an interactive web-response system (IWRS).

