### **6.3.3. Analysis Methods**

The main analysis of categorical efficacy variables and health outcomes variables will use a logistic regression analysis with treatment group in the model. The p-value and 100(1-alpha)% CI for the odds ratio from the logistic regression model are used for primary statistical inference. The difference in percentages and 100(1-alpha)% CI of the difference in percentages using the Newcombe-Wilson without continuity correction will be reported. The p-value from the Fisher's exact test will also be produced as a secondary analysis.

The main analysis for all continuous efficacy and health outcomes variables will use mixed model repeated measures (MMRM) analysis. The model will include treatment, region, baseline disease severity, visit, and treatment-by-visit-interaction as fixed categorical effects and baseline and baseline-by-visit-interaction as fixed continuous effects. An unstructured (co)variance structure will be used to model the between- and within-patient errors. If this analysis fails to converge, the heterogeneous autoregressive [ARH(1)], followed by the heterogeneous compound symmetry (CSH), followed by the heterogeneous Toeplitz (TOEPH) will be used. The Kenward-Roger method will be used to estimate the degrees of freedom. Type III tests for the least-squares means (LSM) will be used for the statistical comparison. The LSM difference, standard error, p-value and 100(1-alpha)% CI will also be reported.

Fisher's exact test will be used for the adverse events (AEs), discontinuation, and other categorical safety data for between-treatment group comparisons. Continuous vital signs, body weight, and other continuous safety variables, including laboratory variables, will be analyzed by an ANCOVA with treatment group and baseline value in the model. The significance of within-treatment group changes from baseline will be evaluated by testing whether or not the treatment group LSM changes from baseline are different from zero; the standard error for the LSM change will also be displayed. Differences in LSM will be displayed, with the p-value associated with the LSM comparison to placebo and a 95% CI on the LSM difference also provided. In addition to the LSMs for each group, the within-group p-value for the change from baseline will be displayed. Treatment-emergent high/low for categorical laboratory safety analyses will also be produced.

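### The primary HiSCR model has treatment group only, so baseline AN count and Hurley stage, already collected before dosing, cannot correct a chance imbalance between two small arms

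*SAP*

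**What the plan says.** SAP 6.3.3 sets the general rule that the main analysis of categorical endpoints "will use a logistic regression analysis with treatment group in the model". SAP 6.7.1 applies it to HiSCR: "The composite endpoint will be analyzed using logistic regression on the mITT and PPS population with treatment group in the model". Fisher's exact test, listed as a secondary analysis, is also unadjusted. Protocol 9.4.2 says logistic regression and names no covariate.

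For continuous endpoints, SAP 6.3.3 is different: "The model will include treatment, region, baseline disease severity, visit, and treatment-by-visit-interaction as fixed categorical effects", plus the baseline value and its interaction with visit.

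On allocation, SAP 5.2 gives a 2:1 ratio and says: "Assignment to treatment groups will be determined by a computer-generated random sequence using an interactive web-response system (IWRS". Neither SAP 5.2 nor Protocol 6.3 names a stratification factor.

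The Schedule of Activities places lesion assessments and Hurley stage at Visits 1 and 2, and inclusion criterion 6 requires an AN count of at least 4. Hurley stage enters a HiSCR model only in the subgroup analyses of SAP 6.10, where it comes with a treatment interaction.

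**The concern.** HiSCR depends on the change in AN count and on abscesses and draining fistulae not increasing, so baseline burden may well predict it. A 50% fall is easier to reach by chance from a low count. As an illustration, with no true change and looking at the AN component alone, a Poisson count meets the 50% cut with probability 24% from a mean of 4 and 7% from a mean of 10. With strong overdispersion (negative binomial, size 2) the figures are 41% and 33%.

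The SAP treats baseline severity as worth adjusting for on continuous endpoints and as a subgroup factor for HiSCR. It leaves severity out of the one test that decides the study and gives no reason. With 42 v 21 participants (Protocol) or 34 v 17 (SAP), chance differences between arms can be sizeable. The planned main analysis has no means of correcting them, and it may also forgo some precision.

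**Working it through.** **Plan's own figure.** Protocol 9.2 says: "This sample size provides at least 80% power to the primary endpoint of HiSCR response", for a two-sided test "with significance level of 0.05". The response rates behind it are blacked out, so it cannot be reproduced. The checks below assume a placebo rate of 25%.

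**Inputs.** From the documents: 42:21 (Protocol 9.2), 34:17 (SAP 6.2), two-sided alpha 0.05, treatment-only model. Assumed, because the documents are silent: Hurley III share 30-50% (40% in the simulations). Assumed prognostic strength, as odds ratios for nonresponse (Hurley III v II; per SD of AN): none (1; 1), weak (1.5; 1.25), moderate (2; 1.5), strong (4; 2).

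**1. How often imbalance occurs.** The SD of the arm difference in Hurley III share is sqrt[p(1-p)(1/n1 + 1/n0)].
- 42:21, p = 0.5: sqrt[0.25 × (1/42 + 1/21)] = 0.134. A 20-point gap is 0.20/0.134 = 1.5 SD, two-sided probability about 13%. Exact binomial: 9.8%, 12.2% and 13.0% for p = 0.3, 0.4 and 0.5.
- 34:17, p = 0.5: sqrt[0.25 × (1/34 + 1/17)] = 0.149. Exact binomial: 16.0%, 18.9% and 19.9%.
- AN count: the SE of the standardized difference is sqrt(1/42 + 1/21) = 0.267, so a gap of at least 0.5 SD has probability 6%. At 34:17 the SE is 0.297 and the probability 9%.

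**2. What imbalance does to the estimate.** Simulation used 6,000 trials per setting. Placebo had at least 20 points more Hurley III in about 6% of trials at 42:21 and 9-10% at 34:17, roughly half the two-sided figures. In those trials the unadjusted risk difference exceeded the truth on average by about 1-4 points (weak), 2-4 (moderate) or 5-7 (strong). The adjusted, standardized difference stayed within about 2 points of the truth.

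Hand check, strong case under no treatment effect: with 40% Hurley III and a 25% overall rate, an odds ratio of 4 gives response rates of 34.0% (II) and 11.4% (III), since 0.6 × 0.340 + 0.4 × 0.114 = 0.25. The gap is 22.6 points. The mean excess, given that it is at least 20 points, is about 26 points (exact binomial). So 0.226 × 0.26 = 0.059, against 0.057 simulated.

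**3. Power, treatment-only to adjusted.**

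| Prognostic strength | 63, 25% v 60%: Wald | 63: LR | 51, 25% v 66%: Wald | 51: LR |
|---|---|---|---|---|
| None | 74.7 to 75.9 | 80.3 to 78.4 | 79.1 to 79.7 | 83.6 to 82.1 |
| Weak | 74.7 to 76.9 | 80.1 to 79.1 | 79.0 to 80.6 | 84.1 to 83.4 |
| Moderate | 74.9 to 77.7 | 79.9 to 80.0 | 78.2 to 80.8 | 83.2 to 83.5 |
| Strong | 74.4 to 82.1 | 79.7 to 84.2 | 78.6 to 84.4 | 83.8 to 87.5 |

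LR is the likelihood-ratio test. Across the settings run, moderate covariates gave about 0 to +4 points. Strong covariates gave about +4 to +8 here, and up to about +9 in a second simulation at 42:21 with log-odds effects of 0.8 and 1.0 on both covariates. The relative efficiency of the risk difference was 0.96-0.99 (none or weak), 1.01-1.02 (moderate) and 1.10-1.15 (strong).

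**4. Type I error.** Wald: about 3-4% with or without adjustment. LR: about 5-6% unadjusted and about 6% adjusted.

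**The case against.** The best defence is that this is a choice about efficiency, not an error, and much of that defence stands. Three stronger readings are tempting, and the documents do not support them.

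- *A reader might infer that the trial certainly gives up power.* Neither document states how prognostic AN count or Hurley stage is, and HiSCR is already relative to each participant's own baseline. With null or weak covariates the likelihood-ratio test loses 1-2 points. Part of the apparent Wald gain arises because the unadjusted Wald test is conservative at this size; it rises by about 1 point even when the covariates are noise.
- *A reader might infer that randomization is unstratified.* The documents say only that the IWRS uses a computer-generated sequence. Silence on stratification does not show that there is none.
- *A reader might infer that the primary test is invalid.* It is not. Its error rate already averages over chance imbalance.

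The SAP also has partial safeguards: baseline disease characteristics are summarized (6.6), Hurley subgroups are modelled (6.10), and the Newcombe-Wilson difference (6.3.3) is on the scale of the stated estimand. None of these is an adjusted estimate of the overall effect. Sparse data are a fair worry too: at a 20-25% rate, 17-21 placebo participants yield about 3-5 responders (0.20 × 17 = 3.4; 0.25 × 21 = 5.3). The fix therefore needs a fallback.

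**Conclusion.** The point holds as a recommended improvement. The treatment-only model is valid but cannot correct a chance imbalance in two baseline measures the trial already collects, and it departs without explanation from how the SAP treats continuous endpoints. A Hurley III gap of at least 20 points would arise in about one trial in ten to one in five. When the excess is in the placebo arm, the effect is overstated on average by 1-4 points with weak or moderate covariates and 5-7 with strong ones. An excess in the active arm should understate it in the same way, though that direction was not tabulated.

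Protection against imbalance is the main argument; power is secondary and conditional. These sizes rest on the assumed 30-50% Hurley III share, a 25% placebo rate and the assumed range of prognostic strength.

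**What to change.** Revise SAP 6.3.3 and 6.7.1 before any unblinding:

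1. Fit the HiSCR logistic model with treatment, log baseline AN count and participant-level baseline Hurley stage (II/III). Hurley stage is recorded by region (Protocol 8.1.1), so define the participant's stage as that of the worst region. Inclusion criterion 4 makes this II or III.
2. Name the standardized (marginal) risk difference with its 95% CI as the primary estimate. SAP 6.1.1 states the estimand as a difference in proportions, whereas SAP 6.3.3 now rests primary inference on the odds ratio. State how the standard error is obtained and which p-value is primary, since the Wald and likelihood-ratio tests behave differently at this size.
3. Use Firth penalization if there is separation or sparse data, and add no further covariates apart from any stratification factors (item 5).
4. Keep the unadjusted Newcombe-Wilson difference and Fisher's exact test as supportive.
5. State whether the IWRS list is stratified and, if so, put its factors in the model.

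The cost is SAP wording and a few lines of code, with no new data. Protocol 9.4.2 names no covariates, so there is no conflict with it, and the SAP needs revising anyway because it still plans 51 participants against the Protocol's 63. Timing matters: SAP 6.12 plans unblinded looks at about 12 and about 21 patients. If one has already taken place, the adjusted model should be a labelled sensitivity analysis. The downsides are a possible loss of 1-2 points of power on the likelihood-ratio test if the covariates prove non-prognostic, and a conditional odds ratio, which the standardized risk difference addresses.
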